At the same time, there are scarce data on several aspects of the use of triple FDCs. In particular, the advantages of triple FDCs in comparison with traditional approach to the treatment require complex investigation with the use of outpatient methods of BP measurement of. The effect of triple FDCs on the quality of life (QOL) of hypertensive patients is also of interest.

AIM AND OBJECTIVES OF THE PROGRAM:

To assess the antihypertensive effectiveness effect on the 24-hour BP profile, as well as tolerability of and compliance to the treatment with a triple FDC of amlodipine / indapamide / perindopril arginine in hypertensive patients in the real clinical practice.

Primary endpoints:

• The effectiveness of triple FDC of amlodipine / indapamide / perindopril arginine in terms of BP control in hypertensive patients from the real clinical practice.

Secondary endpoints:

- The 24-hour BP profile on the top of FDC of amlodipine / indapamide / perindopril arginine in hypertensive patients from the real clinical practice.
- Tolerability of the triple FDC of amlodipine / indapamide / perindopril arginine in hypertensive patients from the real clinical practice.
- Compliance with the treatment with triple FDC of amlodipine / indapamide / perindopril arginine in hypertensive patients from the real clinical practice.

DESIGN AND METHODOLOGY

Type of program: Multicenter, observational, non-controlled, open-label program. **Investigators:** Cardiologists and outpatient (primary care) physicians (general practitioners). **Number of patients:** 1,300 hypertensive patients.

The patient is included in the program if prior to the study his/her doctor decided to adjust treatment, targeted at the BP control improvement, by prescription of a triple FDC of amlodipine / indapamide / perindopril arginine. The prescription of the triple FDC of amlodipine / indapamide / perindopril arginine during the program is made by the doctor's decision according to the instructions for medical use of this FDC.

Presumably, each doctor will include 4 patients in average. It is planned to include 1,300 patients.

Time frame of the program

First subject in (FSI):	November, 2018
Last subject last visit (LSLV):	January, 2019
Database lock:	February, 2019
Statistic report:	May, 2019
Clinical study report:	January, 2020.

Inclusion criteria

- Age 18 to 79 years
- Essential hypertension
- Patient's consent to participate in the program

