• Doctor's decision to prescribe FDC of amlodipine / indapamide / perindopril arginine, according to the instruction for use, prior to the inclusion in the program.

Non-inclusion criteria

- Symptomatic, or secondary arterial hypertension
- Office BP ≥ 180/110 mm Hg on treatment (at V0 visit)
- History of myocardial infarction, unstable angina, or cerebrovascular accident within the past 1 year
- CHF of class III-IV NYHA
- Type I diabetes or decompensated type 2 diabetes
- Diseases with severe organ dysfunction (hepatic failure, renal failure, etc.)
- Contraindications to or known intolerance of dihydropyridine calcium channel blockers (including amlodipine) and/or indapamide and/or ACE inhibitors (including perindopril) and/or their fixed combination
- Inability to understand the nature of the program and/or to follow the doctor's recommendations, including ones for the BP self-monitoring.

During the program it is planned to perform:

- Office BP measurements. Arterial pressure should be measured in accordance with the recommendations of the European Society for Hypertension (ESH) using an auscultatory or oscillometric method and a semiautomatic sphygmomanometer. Before measurements, the patient should be in the sitting position for 3-5 minutes. The BP is measured on each arm, and the arm with the highest BP value is considered as reference one. Three measurements are carried out on the reference arm when patient is in the sitting position, and the average value of the second and third BP measurements with an interval of at least 1-2 minutes is recorded.
- Pulse rate (HR) measurement.
- Ambulatory blood pressure monitoring (ABPM) (in those patients, in whom it is required, according to the decision of treating physician, based on his/her experience and established practice). The BP will be measured on the non-dominant arm. The measurements will be carried out every 15 minutes in the daytime from 7:00 to 23:00 and every 30 minutes in the nighttime from 23:00 to 7:00.

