Defining the inclusion/non-inclusion	Х			
criteria	^			
Patient's informed consent	Х			
Medical history, risk factors and lifestyle	Х			
Recording of the current therapy	Х	Х	Х	Х
BP and HR measurements	Х	Х	Х	Х
Body weight and height	Х			
ABPM (in a part of patients)	Х			Х
Issuing the diaries for BP self-monitoring				
Recoding of the data of BP self-		Х	Х	Х
monitoring		^	^	^
Assessment of adverse events		Х	Х	Х
Completion of the QoL questionnaire	Х			Х
Completion of the Treatment compliance questionnaire	Х			X

Flow chart of the program

Visit 1 (inclusion in the program)

- Selection of patients; defining the inclusion/non-inclusion criteria.
- Providing a patient with the Diary for BP self-monitoring and instruction on its completion.
- Carrying out the following examinations:
 - o BP and HR measurements;
 - \circ $\;$ ABPM (in those patients, to whom it was prescribed by the doctor).
- Recoding of the current therapy; completion of the questionnaires:
 - SF36 questionnaire for the QoL assessment (Appendix 2);
 - Patient's treatment compliance questionnaire (Appendix 3).

Visit 2

- Carrying out the following examinations:
 - o BP and HR measurements;
 - Control of the completion of BP self-monitoring diary by a patient.
- Antihypertensive treatment at the time of visit.
- Assessment of the adverse events.

Visit 3

- Carrying out the following examinations:
 - o BP and HR measurements;
 - o Control of the completion of BP self-monitoring diary by a patient.
- Antihypertensive treatment at the time of visit.
- Assessment of the adverse events.

Visit 4. Completion of the program

- Carrying out the following examinations:
 - o BP and HR measurements;
 - \circ ABPM (in those patients, to whom it was prescribed by the doctor).
- Antihypertensive treatment at the time of visit.
- Completion of the questionnaires:
 - SF36 questionnaire for the QoL assessment (Appendix 2);
 - Patient's treatment compliance questionnaire (Appendix 3).
- Assessment of the adverse events.

• Collection of the diaries of BP self-monitoring.

CONCOMITANT TREATMENT

The treatment with any drugs, including antiplatelets, statins, nitrates, anti-inflammatory or other drugs, is determined by the treating physician.

Diet and physical activity

During the program there will be no additional restrictions of diet or physical activity.

Collecting and reporting the safety data

1. Definitions

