2.3. Responsibilities of sponsor/marketing authorization holder (MAH)

Independently of the regulatory obligations of investigator, the sponsor/MAH must report the pharmacovigilance data to the appropriate authorities in accordance with the Good Vigilance Practice and local regulations.

Cases are closed when an adverse event has recovered or patient's condition was stabilized and the report is deemed sufficiently detailed for adequate medical analysis of the case.

Ethical considerations

The program will be conducted in accordance with the principles of the Declaration of Helsinki, as amended in Fortaleza, Brasil, in 2013. Protocol of program was checked and approved in accordance with the legislation of the Russian Federation and will be complied with by the sponsor, especially with regard to data protection. Patients will be fully informed, and they will need to provide a written consent before participation in the program. Investigator should confirm in the CRF that the patient has provided an informed consent. The "Informed consent" implies that there was an individual discussion with the participant about the nature of the interview and examinations to be conducted.

The sponsor will not have data that allow identification of participants.

The study documents will be approved by the Ethics Committee.

Organizational structure and responsibilities

Investigators will receive informed consent forms and involve participants, ensure data collection in accordance with the protocol, fill in case report forms (CRFs) and verify the accuracy of the information in these CRFs, as much as possible. The patient will be provided with all information to obtain informed consent. At the same time, participants will be asked to provide their consent to the use of their personal data. The data of the participants will remain completely confidential.

Sponsor

The sponsor will be responsible for all stages of the program, for providing the resources necessary to initiate and perform the program in accordance with local regulations, as well as for the validity of the recorded data.

Statistical center

All data will be transferred and centralized by the sponsor.

Effectiveness and tolerability variables:

- Mean change in the office SBP and DBP (in mm Hg) measured in the sitting position

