- Percentage (%) of patients at the target levels of the office BP (SBP <140 mm Hg and DBP <90 mm Hg): in general sample and in subgroups (men, women, patients with IHD, diabetes, metabolic syndrome, ISAH, and patients older than 65 years)
- Change in the proportion of patients with different 24-hour BP profiles (dipper, non-dipper, reduced dipper, extreme dipper, nocturnal hypertension)
- Mean change in the 24-hour SBP and DBP (in mm Hg) in patients who performed ABPM
- Mean change in the daytime SBP and DBP (in mm Hg) in patients who performed ABPM
- Mean change in the nighttime SBP and DBP (in mm Hg) in patients who performed ABPM
- Percentage (%) of patients at the target levels of the office BP (24-hour SBP <135 mm Hg and DBP < 85 mm Hg) in patients who performed ABPM
- Change in the mean score of the SF-36 survey (Appendix 2)
- Changes in the treatment compliance score by the Compliance questionnaire (Appendix 3)
- List of SAEs
- List of AEs
- List of AEs that resulted in the withdrawal of the triple FDC of amlodipine / indapamide / perindopril arginine.
- List of ADR
- List of SADR
- List of special situations

Statistical parameters

All parameters will be analyzed using the methods of descriptive statistics. For each parameter, the number of patients, mean, standard error, minimum and maximum values will be indicated.

Statistical analysis

- The baseline characteristics will be analyzed in all the patients who started the treatment (intention-to-treat [ITT] population). In case of significant differences between two treatment groups, the baseline characteristics will be provided for both of them.
- Changes in the SBP and DBP (with the corresponding confidence intervals) will be assessed in the patients who completed the program without major deviations from protocol (per-protocol population [PPP]).
- The analysis of parameters with normal distribution will be performed using the Student's t-test for paired measurements; otherwise the non-parametric Wilcoxon test will be used. The percentage of patients with normalized BP, as well as the percentage of patients who responded to treatment (with 95% confidence intervals), will be calculated.
- Questionnaires: The score for each scale will be calculated as the sum of scores for questions constituting the scale.
- Assessment of the AEs will be carried out in all the patients who started the treatment (ITT population).

Administrative aspects

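### The planned paired t-test and Wilcoxon test treat patients as independent although about 4 patients per doctor are presumed; if outcomes correlate within doctor, intervals will be somewhat too narrow

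*Combined protocol and SAP*

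**What the plan says.** Design and methodology describes a "Multicenter, observational, non-controlled, open-label program" run by cardiologists and primary care physicians. On size it says: "Presumably, each doctor will include 4 patients in average. It is planned to include 1,300 patients".

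Statistical parameters says that for each parameter "the number of patients, mean, standard error, minimum and maximum values will be indicated". For normally distributed parameters, Statistical analysis plans Student's "t-test for paired measurements; otherwise the non-parametric Wilcoxon test will be used". The same section asks for confidence intervals for the SBP and DBP changes in the per-protocol population, and for 95% intervals for the percentages of patients normalised and responding. In Appendix 2, the requirements for presenting results ask for a confidence interval and a P value for the main results.

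The plan names the tests but gives no method for the standard errors or intervals. No doctor or centre term, mixed model, GEE, robust variance, design effect or ICC appears in the text.

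**The concern.** The plan describes recruitment in small groups, one per doctor, and then names tests that ignore the grouping. Patients of one doctor may resemble each other through case mix and practice, and the protocol leaves room for this:

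- Office BP may be taken "using an auscultatory or oscillometric method and a semiautomatic sphygmomanometer".
- Treatment with other drugs "is determined by the treating physician".
- ABPM is done "according to the decision of treating physician, based on his/her experience and established practice", so ABPM patients may be concentrated in certain practices.

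With a positive within-doctor correlation, 1,300 patients carry less information than 1,300 independent ones, and an unclustered standard error is too small. The program has no control arm, so an estimate with its interval is its main statistical output. What is at stake is whether an interval labelled 95% covers about 95%.

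**Working it through.** **Inputs from the document:** 1,300 patients; average m = 4 per doctor (Design and methodology). This gives 1,300 / 4 = 325 doctors. The plan gives no derivation of 1,300, so there is no sample-size figure to reproduce.

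**Assumptions (not in the document):** ICC 0.01 to 0.10; coefficient of variation (CV) of patients per doctor 0, 0.5 or 1.0; SD of SBP change 15 mm Hg; control rate 70%; 80% of patients completing, at random, where stated.

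**Formulas**
- Design effect: DE = 1 + [m(1 + CV²) − 1] × ICC
- Widening of a correct interval: √DE − 1
- True coverage of a nominal 95% interval: 2Φ(1.96/√DE) − 1

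**Step 1. Exactly 4 per doctor (CV = 0), all 1,300: DE = 1 + 3 × ICC**

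| ICC | DE | Widening | Coverage |
|---|---|---|---|
| 0 | 1.00 | 0% | 95.0% |
| 0.01 | 1.03 | 1.5% | 94.7% |
| 0.05 | 1.15 | 7.2% | 93.2% |
| 0.10 | 1.30 | 14.0% | 91.4% |

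**Step 2. Uneven enrolment, ICC 0.10.** The figure of 4 is a presumed average, and equal clusters are the mildest case.
- CV 0.5: m(1 + CV²) = 4 × 1.25 = 5; DE = 1 + 4 × 0.10 = 1.40; 18% wider; coverage 90.2%.
- CV 1.0: 4 × 2 = 8; DE = 1 + 7 × 0.10 = 1.70; 30% wider; coverage 86.7%.

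**Step 3. Completers only.** If 80% of each doctor's 4 patients complete at random, the mean is 3.2 and the variance 0.64. Then E[m²]/E[m] = (0.64 + 10.24)/3.2 = 3.4, and DE = 1 + 2.4 × ICC. At ICC 0.10, DE = 1.24: 11.4% wider, coverage 92.2%.

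**Step 4. Absolute size at ICC 0.10, equal enrolment**
- SBP change, all 1,300: 1.96 × 15/√1,300 = 0.82; × 1.140 = 0.93 mm Hg.
- SBP change, 1,040 completers: 1.96 × 15/√1,040 = 0.91; × 1.114 = 1.02 mm Hg.
- Control rate, all 1,300: 1.96 × √(0.21/1,300) = 2.49 points; × 1.140 = 2.84.
- Control rate, 1,040 completers: 1.96 × √(0.21/1,040) = 2.79 points; × 1.114 = 3.10.

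The half-width therefore grows by about 0.1 mm Hg, or by 0.3 to 0.4 percentage points.

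**Step 5. Simulation check of the named tests.** With 325 doctors of 4 patients and normal data, a nominal 5% test rejects a true null as follows (4,000 runs for the t-test, 2,000 for Wilcoxon):

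| ICC | Paired t-test | Wilcoxon |
|---|---|---|
| 0 | 5.2% | 5.5% |
| 0.05 | 6.3% | 6.0% |
| 0.10 | 8.3% | 8.8% |

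Switching to the rank test does not remove the problem. With 325 doctors, a doctor-clustered interval covers about 95% in simulation, both at ICC 0 and at ICC 0.10.

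**Step 6. Centre level.** The document does not give the number of centres. In simulation, a plain robust interval clustered on only 10 centres covers about 92% when centres are of equal size, and about 87% when they are unequal (the latter with an assumed centre ICC of 0.02). Clustering on few centres therefore needs a small-sample correction.

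**The case against.** The strongest objection is that the defect depends on a quantity the documents do not give, and that there are reasons to expect it to be small. All patients receive one fixed combination under common eligibility criteria, with one office BP procedure and one target. A constant difference between auscultatory and oscillometric readings largely cancels in a within-patient change, so it bears mainly on the control rate. The choice of who has ABPM determines who enters that subset; it does not in itself make BP outcomes alike. This stands: the ICC may be small, and the point must stay conditional. It is not a reason to assume zero, because the choice of other drugs and the case mix may still differ between doctors.

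The second objection is weight. The program is descriptive, with no between-group test, power claim or success threshold, and the absolute effect is small. This also stands, and it sets the priority.

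A reader might infer more than the text supports:

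- **That the plan prescribes wrong intervals.** It prescribes tests that assume independence. On how the standard errors and intervals are computed it is silent.
- **That outcomes are known to cluster by doctor.** Nothing in the documents shows this.
- **That 1.5 to 14% bounds the effect.** It does not. It assumes exactly 4 patients for every doctor, and Step 2 gives larger values.
- **That the program's findings are in doubt.** A large mean BP change would remain significant under any of these ICCs.

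**Conclusion.** The concern holds as a low-priority improvement. Both named tests assume independent patients, the plan has no doctor or centre term, and it presumes about 4 patients per doctor. If outcomes correlate within doctor, nominal 95% intervals will cover somewhat less than 95%: 94.7 to 91.4% at an assumed ICC of 0.01 to 0.10 with equal enrolment, and 90.2 to 86.7% at ICC 0.10 with an assumed CV of 0.5 to 1.0. These are illustrations that rest on the assumed ICC and CV. At ICC 0 essentially nothing changes. Clustering in itself does not alter the point estimates, and no decision rule depends on the intervals, so what improves is the honesty of the error bars.

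**What to change.** In Statistical analysis:

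1. State that the confidence intervals and tests for office BP change, and the 95% intervals for the percentages normalised and responding, use doctor-clustered robust variance or a bootstrap that resamples doctors.
2. Apply the same method to the ABPM and questionnaire changes where inference is reported.
3. Where a rank test is kept, for example for the six-question compliance score, use a clustered signed-rank test.
4. If several doctors share a centre, clustering may be moved to centre level. When centres are few, do so only with a small-sample correction, for example a t reference with centres minus 1 degrees of freedom and a bias-corrected variance.
5. Confirm before database lock that a doctor code and a centre code are held for each patient. Under Statistical center the document says only "All data will be transferred and centralized by the sponsor". The event form in Appendix 1 asks for the doctor's name, but only on event reports.

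**Cost:** a few sentences of SAP wording, minor extra analysis work, and somewhat wider intervals. The statistical packages listed in Appendix 2 are only recommended, so other software can be used. No visit or patient procedure changes. If the codes are not in the database, they must be added before lock.

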2. Role physical (RP)	4A, 4B, 4C, and 4D	3 – 8	4
3. Bodily pain (BP)	7 and 8	2 – 12	10
4. General health (GH)	1, 11A, 11B, 11C, and 11D	5 – 25	20
5. Vitality (VT)	9A, 9E, 9G, and 9I	4 – 24	20
6. Social functioning (SF)	6 and 10	2 – 10	8
7. Role emotional (RE)	5A, 5B, and 5C.	3 - 6	3
8. Mental health (MH)	9B, 9C, 9D, 9F, 9H.	5 – 30	25

For items 6, 9A, 9E, 9D, 9H, 10, and 11, the count-down is applied.

The formula for calculating the values:

[(actual value of the scale) – (minimal possible value on the scale] : (possible range of values) \Box 100.

Requirements for presenting the results:

- 1. Number of cases per each parameter should be indicated;
- 2. Descriptive statistics: M ± SD, Me (LQ; UQ), % (n/N);
- 3. Accuracy of results (estimates, P value); Confidence interval (for main results of the study) and P value;
- 4. Statistical methods (parametric and non-parametric) and statistical packages should be mentioned.

The recommended statistical packages for the data processing are StatSoft Statistica v.6.0, and SPSS 9.0.

Assessment of patient's compliance with medical therapy [12].

Question	YES	NO
Did you forget to take your medication this morning?		
Since the last visit to the doctor, have you run out of your medication?		
Have you ever taken your medication later than the usual time?		
Have you ever not taken your medication because, on some days, you forgot about it?		
Have you ever not take your medication because you had the impression that it was doing		
more harm than good?		
Do you think that you have too many tablets to take?		

Answer "No" to all the questions: good compliance;

Answer "Yes" to 1-2 questions: minor compliance;

Answer "Yes" to 3 or more questions: noncompliance.

References

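### An unspecified normality check chooses between the paired t-test and Wilcoxon, and Wilcoxon does not test the mean changes that the plan reports

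*Combined protocol and SAP*

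**What the plan says.** The Statistical analysis section makes the test depend on the observed distribution: "The analysis of parameters with normal distribution will be performed using the Student's t-test for paired measurements"; "otherwise the non-parametric Wilcoxon test will be used". It does not name a normality test, a threshold or a graphical criterion. It also does not say whether normality is judged on the within-patient differences or on the values at each visit.

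The list of effectiveness and tolerability variables is written in terms of means. It opens with "Mean change in the office SBP and DBP (in mm Hg) measured in the sitting position" and goes on to mean changes in 24-hour, daytime and nighttime pressure, change in the mean SF-36 score, and change in the compliance score. Under Statistical parameters the summary is again built on the mean: "For each parameter, the number of patients, mean, standard error, minimum and maximum values will be indicated". A median with quartiles is asked for only in the reporting requirements of the SF-36 appendix.

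Confidence intervals are planned for BP change, in per-protocol completers, but no interval is tied to the Wilcoxon test. On size, the plan says "It is planned to include 1,300 patients". Ambulatory monitoring is done in only part of the sample, and the number is not given.

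**The concern.** Three features combine.

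- **The rule is not reproducible.** Two analysts can follow it and reach different tests for the same variable, because neither the check nor the quantity checked is defined.
- **Formal normality checks become very sensitive at this sample size.** The paired t-test, by contrast, no longer needs normal differences. The check is most likely to reject where its answer matters least for the validity of the t-test.
- **The switch changes the question.** Signed-rank Wilcoxon is centred on the pseudomedian (the median of pairwise averages of the changes). This equals the mean only when the changes are symmetric. With skewed changes, the table would show a mean, its standard error and a P value that does not refer to that mean.

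At stake is the reading of variables whose true change may be small: the SF-36 scales, the compliance score and possibly the ambulatory values. There, a significant P value could stand beside a mean change of zero.

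**Working it through.** **Inputs.** From the plan: 1,300 patients, the switching rule, and mean change as the effect measure. The 1,300 is stated without a derivation, so there is no figure to reproduce. Assumed, because the plan does not give them: two-sided 5% level, SD of change 10 to 18 mm Hg, and all distribution shapes.

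**Step 1: how often the rule switches at n = 1,300** (500 simulated samples per cell, each check at 5%).

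| Shape of the changes | Shapiro-Wilk | D'Agostino-Pearson | Lilliefors |
|---|---|---|---|
| Exactly normal | 7% | 5% | 5% |
| Normal, SD 14, rounded to 1 mm Hg | 13% | 5% | 61% |
| Normal, SD 14, rounded to 5 mm Hg | 100% | 5% | 100% |
| Gamma, skewness 0.1 | 22% | 21% | 9% |
| Gamma, skewness 0.2 | 73% | 74% | 38% |
| Gamma, skewness 0.3 | 98% | 98% | 74% |
| Gamma, skewness 0.5 | 100% | 100% | 99% |
| t, 20 df | 49% | 56% | 11% |
| t, 10 df | 95% | 96% | 57% |

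The range is about 5% to 100%. At n = 300 and skewness 0.3 the three rates fall to 42%, 39% and 19%.

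Some listed scores cannot be normal. By the SF-36 appendix, raw role emotional has a range of 3, so its change can take only 7 values (-3 to +3). Raw role physical has a range of 4, giving 9 values. A count of six yes/no compliance items gives 13.

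**Step 2: distance between the two targets.** Take changes with mean 0, SD 1 and skewness g. The average of two independent changes has SD 1/√2 and skewness g/√2. Using median ≈ mean - skewness × SD / 6, the pseudomedian is about -(g/√2)(1/√2)/6 = -g/12. For g = 0.2, 0.3, 0.5 and 1.0 this gives -0.017, -0.025, -0.042 and -0.083 SD. Simulation gives -0.0165, -0.0257, -0.0414 and -0.0829. At SD 14 mm Hg these are 0.23, 0.36, 0.58 and 1.16 mm Hg in size.

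**Step 3: rejection rates with a true mean change of zero, n = 1,300.** As a hand check, Wilcoxon has efficiency about 3/π = 0.955 relative to the t-test near normality. So d = gap × √(0.955 × 1,300) = gap × 35.2, and the rejection rate is about Φ(-1.96 + d) + Φ(-1.96 - d).

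| Skewness | d | Wilcoxon, by hand | Wilcoxon, simulated (1,500 runs) | t-test, simulated |
|---|---|---|---|---|
| 0.2 | 0.58 | 9% | 9.1% | 5.0% |
| 0.3 | 0.91 | 15% | 13.5% | 5.1% |
| 0.5 | 1.46 | 31% | 30.9% | 4.2% |
| 1.0 | 2.92 | 83% | 83.5% | 4.5% |

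A repeat simulation gave about 8%, 16%, 30% and 82% for Wilcoxon and 4-6% for the t-test.

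**Step 4: smaller samples.** At n = 200 and skewness 0.3, d = 0.0257 × √(0.955 × 200) = 0.36 and the hand formula gives 6.5%. Simulation also gives 6.5%, with a switch rate of 31%.

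**Step 5: the mean-based analysis.** The 95% CI half-width for the mean is 1.96 × SD / √1,300, that is 0.54, 0.76 and 0.98 mm Hg at SD 10, 14 and 18. No switch is needed for validity at this size.

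**The case against.** The strongest case against is that little depends on this rule. The program is observational and uncontrolled, the analysis is largely descriptive, and no hypothesis or alpha is stated. BP control is defined as office BP below 140/90 mm Hg, a proportion that uses neither test. Large office BP falls are significant under both. The mean and standard error are reported whichever test is chosen, confidence intervals are planned for BP change, and the appendix adds the median and quartiles. All of this stands and limits the impact. It does not repair a P value that refers to a different quantity from the mean beside it.

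Further points stand in whole or in part:

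- The Wilcoxon figures in Step 3 are not type I errors of that test. It correctly detects a non-zero pseudomedian. The fault is the mismatch with the reported estimate.
- The 1,300 is planned enrolment. BP change uses per-protocol completers, and ambulatory change uses a subset of unstated size, so both the switch rate and the divergence are lower there.
- Rounding to 5 mm Hg is not quite the protocol's situation, since office BP is the average of two readings. Readings rounded to 5 then fall on a 2.5 mm Hg grid. Shapiro-Wilk still rejects 100% on that grid, but D'Agostino-Pearson does not react to rounding (5% even at 5 mm Hg).
- A rank test is a defensible choice for coarse scores, and normality of the change is a natural reading of the rule. Both are reasons to write the choice down.

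A reader might infer that the method would also vary between subgroups. The documents do not support this: subgroups are listed only for the percentage at target office BP, which uses neither test.

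**Conclusion.** The concern holds as a mismatch between test and estimate, created by an undefined data-driven rule. With a true mean change of zero at n = 1,300, the Wilcoxon arm of the rule rejects in about 8-9% of samples at skewness 0.2, 13-16% at 0.3, 30% at 0.5 and 82-83% at 1.0, where the paired t-test stays at about 4-6%. These figures rest on gamma-shaped changes and a two-sided 5% level. The plan gives no distribution, so they illustrate the mechanism and do not predict this dataset. The continuous gamma model also does not represent the coarse scores.

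A reader might go further and conclude that at about 1,300 patients nearly every variable would end up with Wilcoxon. The documents do not support that: they name no check and give no SD or shape, and changes close to normal would mostly keep the t-test under some checks.

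The consequence is confined to secondary variables with small or skewed changes. Conclusions on large office BP falls and on the percentage at target do not change.

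**What to change.** Replace the switching sentence in the Statistical analysis section with one prespecified analysis:

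- For every continuous change variable, report the mean within-patient change with its 95% CI and a paired t-test, whatever the distribution.
- Report the Wilcoxon signed-rank test with a Hodges-Lehmann estimate as a sensitivity analysis, including for role physical, role emotional and the compliance score.
- If the ambulatory subset proves small, use a bootstrap CI for its mean changes.

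The cost is SAP wording only, with no new data. The small downside is some loss of efficiency if the changes are heavy-tailed, which the sensitivity analysis would show.
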